4.2.5.5 Sensitivity Analyses of the Secondary Endpoint

Not applicable.

4.2.5.6 Supplementary Analyses of the Secondary Endpoint

Not applicable.

4.2.5.7 Subgroup Analyses

Not Applicable

4.2.6 Secondary Endpoint – Cough VAS

4.2.6.1 Definition

Participants will be asked to complete a cough severity VAS (100-point linear scale marked with a horizontal or vertical line by the patient, with 0 representing "no cough" and 100 representing "worst cough") measuring subjective assessment by the patient of the prior 24 hours for severity of cough symptoms.

The Cough VAS will be completed each morning in the e-Diary until Week 24.

4.2.6.2 **Derivations**

Change from baseline in Cough VAS average score to Weeks 12 and 24 will be calculated as specified in Section 3.3.1.2.

4.2.6.3 Handling of Dropouts

The 'while-on treatment' strategy will be used: which means that if an intercurrent event occurs all subsequent data for that participant are excluded from the evaluation.

4.2.6.4 Primary Analysis of Secondary Endpoint

Observed values and absolute change from baseline up to Weeks 12 and 24 in Cough VAS average score will be summarised by each intervention group for the FAS population.

Change from baseline to Weeks 12 and 24 in Cough VAS average score will be analysed using a MMRM as described in Section 3.4.3.

LSMean change from baseline and two-sided 90% CI up to Weeks 12 and 24 in Cough VAS average scores will be presented in figures. For primary analysis, LSMean change from baseline through Weeks 12 and 24 in Cough VAS average score will be presented.

A listing including results from the Cough VAS average score will be produced for the FAS population.

4.2.6.5 Sensitivity Analyses of the Secondary Endpoint

Not applicable.

4.2.6.6 Supplementary Analyses of the Secondary Endpoint

Not applicable.

4.2.6.7 Subgroup Analyses

Not Applicable.

4.2.7 Secondary Endpoint – Total CAT measured in clinic

4.2.7.1 Definition

COPD Assessment Test (CAT) is designed to measure how COPD impacts on a patient's daily life and how this might change over time. It consists of 8 questions that ask the patient to rate items relating to symptoms and impact on quality of life (such as normal activity and sleep). Each question is performed on a 5-point Likert scale from 0 (no symptoms/no impact) to 5 (severe symptoms/impact). The CAT will be completed by participants at on-site visits using the e-Diary.

4.2.7.2 **Derivations**

Change from baseline in total CAT score to Week 12 and Week 24 will be calculated as specified in Section 3.3.1.2.

4.2.7.3 Handling of Dropouts

The 'while-on treatment' strategy will be used: which means that if an intercurrent event occurs all subsequent data for that participant are excluded from the evaluation.

4.2.7.4 Primary Analysis of Secondary Endpoint

Observed values and absolute change from baseline up to Weeks 12 and Week 24 in CAT score will be summarised by each intervention group for the FAS population.

Change from baseline through Weeks 12 and 24 in total CAT score will be analysed using MMRM (see details in Section 3.4.3).

LSMean change from baseline and two-sided 90% CI for Weeks 12 and 24 in total CAT score will be presented in figure.

The number and percentage of participants with a change from baseline of -2 or less will be summarised by intervention group.

The total CAT score will be listed by patient for the FAS population.

The analysis will be focused on the FAS population.

4.2.7.5 Sensitivity Analyses of the Secondary Endpoint

Not applicable

4.2.7.6 Supplementary Analyses of the Secondary Endpoint

Not applicable

4.2.7.7 Subgroup Analyses

Not Applicable

4.2.8 Tertiary/Exploratory Endpoint – Cough frequency

4.2.8.1 Definition

The assessment of 24-hour coughs per hour (i.e., average hourly cough frequency based on 24-hour sound recordings) will be evaluated at Visit SV3 (start of treatment) and Visit SV5 (after 12 weeks of treatment) using the VitaloJAK® Cough Monitor device for a subset of participants (up to approximately 50 participants from each arm) from selected sites enrolled in the cough substudy. Data from the device will be filtered for voice frequencies, and speech will not be analysed. If the first recording is successful but the Week 12 recordings are not usable, the Week 12 assessment can be repeated as soon as possible but no later than Week 18. If the first recording at baseline is unsuccessful, the Week 12 recording can be omitted.

More details about VitaloJAK® Cough Monitor device can be found in the Objective Cough Endpoint documentation.

4.2.8.2 Derivations

Change from start of treatment in cough frequency to Week 12 will be expressed as baseline scale ratio (BSR) due to the log-normality of the data.

 $BSR = \exp(\ln Post \ Baseline - \ln Baseline)$

4.2.8.3 Handling of Dropouts

Participants who drop out study early or had intercurrent events will be included for analysis using treatment policy strategy.

Treatment policy strategy means if an intercurrent event occurs all subsequent data for that participant up to last dose are included in the evaluation.

4.2.8.4 Primary Analysis of Tertiary/Exploratory Endpoint

Observed values and BSR cough frequency will be summarised with the statistics planned for log-normal data for 24h, waking and sleeping. For cough frequency parameters (24-hour, waking and sleeping) the values will be log-transformed (to base e) after adding an offset of 0.005 to bring all data above zero.

BSR cough frequency at Week 12 will be analysed using ANCOVA model for 24-hour, waking and sleeping. The response variable will be the ln(BSR cough frequency) at Week 12 with study intervention as factor for comparison of AZD4831 and placebo, ln(baseline value) as a covariate, and region will be added as a random covariate.

The reportable results from the ANCOVA are the ones described in Section 3.4.2, by back-transforming all the results (i.e. LSMean, CI), except the p-value.

Distributions of 24-hour, waking and sleeping cough frequency at baseline and Week 12 will be displayed by study intervention group with box-plots.

The average 24-hour, waking and sleeping cough frequency will also be listed by patient.

All these analyses will be based on the cough subset population.

4.2.8.5 Sensitivity Analyses of the Tertiary/Exploratory Endpoint

Not applicable

4.2.8.6 Supplementary Analyses of the Tertiary/Exploratory Endpoint

Not applicable

4.2.8.7 Subgroup Analyses

Not Applicable

4.2.9 Tertiary/Exploratory Endpoint – Change from baseline in spirometry endpoints measured face to face

4.2.9.1 Definition

Data collected will include, but are not limited to, absolute and % predicted (as applicable) PEF, FEV1, FVC, FEV1/FVC, forced mid-expiratory flow (FEF25-75%), and inspiratory capacity. The following parameters will be included in the analysis PEF, FEV1, FVC, FEV1 and FVC % predicted, FEV1/FVC, forced mid-expiratory flow (FEF25-75%) and forced inspiratory vital capacity. At SV3 and SV5, face-to-face spirometry will be undertaken at the site, followed by virtual spirometry. At SV4 and SV7, virtual spirometry will be performed away from the study site prior to attendance at the site and then face-to-face spirometry will be performed subsequently once the participant has attended the site.

4.2.9.2 Derivations

Change from baseline in spirometry endpoints to Weeks 4, 12 and 24 will be calculated as specified in Section 3.3.1.2.

4.2.9.3 Handling of Dropouts

Participants who had intercurrent events will be included for analysis using "treatment policy" strategy.

4.2.9.4 Primary Analysis of Tertiary/Exploratory Endpoint

Observed values and absolute change from baseline up to Weeks 4, 12 and 24 in spirometry endpoints will be summarised by each intervention group for the FAS population.

Change from baseline through Week 24 in spirometry endpoints for participants with moderate to severe COPD will be analysed using MMRM as described in Section 3.4.3.

Spirometry endpoints measured face to face will be summarised.

Spirometry assessments measured face to face will be listed.

The analysis will be focused on the FAS population.

4.2.9.5 Sensitivity Analyses of the Tertiary/Exploratory Endpoint

Not applicable.

4.2.9.6 Supplementary Analyses of the Tertiary/Exploratory Endpoint

Not applicable.

4.2.9.7 Subgroup Analyses

Not applicable.

4.2.10 Tertiary/Exploratory Endpoint – Annualised rate of COPDCompEx Event

4.2.10.1 Definition

The COPDCompEx definition and derivation are detailed in AZ Business Rules.

Events regardless of what type (i.e., acute worsening or exacerbation) must be separated by at least 14 days in order to count as separate events (i.e., there must be at least 14 days during which no criteria for events are fulfilled).

The time during the event and the 14 days after each event will not be considered when defining time at risk for the COPDCompEx event rate. Time at risk (days) will be defined as

[Date of last dose of study intervention – date of the first dose of study intervention] + 2 – recovery time.

Where recovery time is defined as:

$$\sum_{i=1}^{k} [min(i^{th} event end date + 14, date of last dose of study intervention) - i^{th} event start date + 1]$$

4.2.10.2 **Derivations**

Annualised rate of COPDCompEx events, based on the period from baseline to last dose, will be calculated as:

Annualised rate of COPDCompEx events

Total number of COPDCompEx events

Total number of COPDCompEx events

(Date of last dose of IP – Date of the first dose of IP – recovery time + 2)/365.25

For participants who do not experience an on-treatment COPDCompEx event, date of censoring will be the last dose date or last date of eDiary recording whichever is earlier.

For CompEx analyses, only on-treatment events (i.e., events occurring from randomisation up to and including the last dose day) will be considered.

4.2.10.3 **Handling of Dropouts**

The "while on treatment" strategy, same as defined in section 4.2.1.3.

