9.4.2.2 Secondary Endpoints

A similar approach to that described for the primary efficacy endpoint will be applied to the secondary endpoint: time to first exacerbation.

In order to ensure that the same event is not counted twice, concurrent moderate or severe COPD exacerbations with start and stop dates ≤ 7 days apart will be considered the same event and assigned the maximum severity between the two. Time during an exacerbation or in the 7 days following an exacerbation will not be included in the calculation of time at risk. However, the start day of a COPD exacerbation will not be excluded from the time at risk.

Any COPD exacerbation that occurs within 7 days of the last dose of systemic corticosteroids (oral, intramuscular, intravenous) or antibiotics or the last day of hospitalisation or emergency room visit for a prior COPD exacerbation will be combined and counted as a single exacerbation event and as the maximum severity between the individual events. Further details on combining exacerbation events will be provided in the SAP. Consistent criteria will be applied to all exacerbation endpoints.

Plasma concentrations will be summarised by timepoint in all participants. Pharmacokinetic data for those participants with additional PK sampling at Visit SV5 will be used to derive plasma PK parameters such as C_{max} and t_{max} .

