4.2.11.2 Derivations

Annualised rate of moderate or severe COPD exacerbations based on the period during the intervention from baseline through the last dose will be calculated as follows:

Annualised rate of moderate or severe COPD exacerbations

Total number of moderate or severe COPD exacerbations

(Date of last dose of IP – Date of the first dose of IP – recovery time + 2)/365.25

Where recovery time is defined as:

$$\sum_{i=1}^{k} [min(i^{th} \ exacerbation \ end \ date + 7, date \ of \ last \ dose \ of \ study \ intervention)$$

$$- i^{th} \ exacerbation \ start \ date + 1]$$

For participants who do not experience an on-treatment moderate or severe COPD exacerbation event, date of censoring will be the date of last dose.

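### The time-at-risk formulas for the two annualised rates miscount days by adding 2 for everyone, and the SAP sets no single end of follow-up for events and time

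*SAP*

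**What the plan says.** **Day count.** SAP 4.2.10.1 states for COPDCompEx: "The time during the event and the 14 days after each event will not be considered when defining time at risk". Its formula is the bracketed difference "Date of last dose of study intervention – date of the first dose of study intervention] + 2 – recovery time". Recovery time is the sum, over events, of min(event end + 14, last dose) − event start + 1. SAP 4.2.11.2 repeats the form for moderate or severe exacerbations, "Date of last dose of IP – Date of the first dose of IP – recovery time + 2)/365.25", with 7 days in place of 14.

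Protocol 9.4.2.2 also leaves exacerbation time and the next 7 days out of the time at risk, but adds that "the start day of a COPD exacerbation will not be excluded from the time at risk" and that "Consistent criteria will be applied to all exacerbation endpoints". The protocol has no COPDCompEx rate. The SAP amendment history records both rate analyses as additions not in line with the protocol. It also records a later update of the time-at-risk calculation, made for participants whose event lasts from start to end of treatment.

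**End of follow-up.** The SAP makes four statements:
- 4.2.10.2 counts COPDCompEx events up to and including the last dose day.
- 4.2.10.2 says, only for participants with no on-treatment event, that the "date of censoring will be the last dose date or last date of eDiary recording whichever is earlier".
- 4.2.10.3 and 4.2.11.3 apply while-on-treatment handling by reference to 4.2.1.3 and 4.2.2.3. Those sections censor at the intercurrent event and are written for time to first event.
- 3.4.4 uses all available data regardless of treatment discontinuation, with log time at risk as the offset of the negative binomial model.

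**The concern.** Days on treatment, counted inclusively, are last dose − first dose + 1. A constant of 2 adds a day that no rule in either document supports for someone with no event. Each recovery term removes the event's start day, so the single extra day can restore only one start day, however many events there are. The size and sign of the error may therefore depend on the outcome being analysed.

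The end date is a separate matter. In a rate model the count and the offset must cover the same period. If programmers stop counting events at the intercurrent event, as 4.2.10.3 and 4.2.11.3 suggest, but take the offset from the printed formula, the denominator contains time in which no event could be counted. That lowers the rate, and it lowers it more in the arm with more early intercurrent events.

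**Working it through.** The documents print no worked value for time at risk, so there is no stated figure to reproduce.

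**Inputs.** F = first dose day; L = last dose day; k events with start s and end e; w = 14 (4.2.10) or 7 (4.2.11); m = min(e + w, L). Treatment lasts 84 to 168 days (12 to 24 weeks, SAP 3.3). Recovery windows are taken not to overlap. For COPDCompEx this follows from the separation rule: "there must be at least 14 days during which no criteria for events are fulfilled".

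**Three counts**
- SAP formula: (L − F) + 2 − Σ(m − s + 1)
- Start day kept (protocol, exacerbations): (L − F) + 1 − Σ(m − s)
- All event days removed (the sentence in SAP 4.2.10.1): (L − F) + 1 − Σ(m − s + 1)

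SAP minus start-day-kept = 1 − k days. SAP minus all-event-days-removed = 1 day for every k. Neither difference depends on event length or window.

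**Day-by-day check, 168 treatment days** (10-day events for k = 1 to 3, 6-day events for k = 4):

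| Events | w | SAP | Start day kept | All event days removed |
|---|---|---|---|---|
| 0 | either | 169 | 168 | 168 |
| 1 | 14 | 145 | 145 | 144 |
| 2 | 14 | 121 | 122 | 120 |
| 3 | 14 | 97 | 99 | 96 |
| 4 | 14 | 89 | 92 | 88 |
| 1 | 7 | 152 | 152 | 151 |
| 2 | 7 | 135 | 136 | 134 |
| 3 | 7 | 118 | 120 | 117 |
| 4 | 7 | 117 | 120 | 116 |
| one spanning all treatment | either | 1 | 1 | 0 |

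For event-free participants the excess is 1/168 = 0.6%, or 1/84 = 1.2% (85 against 84). With two 6-day events in 84 days and w = 7, the SAP gives 59 against 60 days, or −1.7%.

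**Window.** Take an event-free participant with an intercurrent event on day 42 who keeps dosing. The printed denominator is 85 or 169 days, against 42 if time stops at that event: 85/42 = 2.0 times, 169/42 = 4.0 times.

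**Effect on the rate ratio.** This was simulated on assumed inputs, none taken from trial data. They were a placebo rate of about 2 per year, an underlying ratio of 0.7, 7-day events, w = 14, 84 to 168 days of dosing, 8,000 participants per arm, and intercurrent events at a random day from day 14 with dosing continuing. Ratios are total events over total time, so each comparison should be read within its row.

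| Early intercurrent events, placebo / active | All events, SAP day count | All events, start day kept | Events to intercurrent event, time to last dose | Events and time to intercurrent event |
|---|---|---|---|---|
| 10% / 10% | 0.712 | 0.713 | 0.718 | 0.719 |
| 5% / 15% | 0.725 | 0.726 | 0.689 | 0.724 |
| 10% / 20% | 0.715 | 0.716 | 0.680 | 0.714 |

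The day-count error moves the ratio by about 0.001. The window mismatch moves it by about 0.001 when balanced, and by about 0.03 under the assumed imbalances.

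**The case against.** The +2 is deliberate. With +1, an event covering all of treatment would leave zero days and an undefined log offset, and the amendment history gives that case as the reason for the update. Under the start-day rule +2 is also exact for one event. This stands as an explanation, but it does not justify giving the extra day to participants with no event.

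A reader might infer that the COPDCompEx formula breaks the protocol by losing k − 1 days. The documents do not support that. The start-day sentence concerns COPD exacerbations, and its stated reach is exacerbation endpoints. It binds 4.2.11.2 directly and reaches 4.2.10 only by analogy. For COPDCompEx the governing text is the SAP's own sentence, against which the error is one day at every k.

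A reader might also infer that events definitely stop counting at the intercurrent event or last diary, so that the denominator is plainly too long. That too goes beyond the text. SAP 4.2.10.2 counts events to the last dose day, the same end as the offset. The diary cut-off covers only event-free participants, and the intercurrent-event cut-off comes through first-event rules. Treatment discontinuation should normally fall at about last dose, so mainly prohibited medication can open a gap. Nor is time after the last diary wholly unobservable, because exacerbations and dropout for lack of efficacy also count as COPDCompEx events. What stands is that the sections conflict.

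**Conclusion.** Both formulas are wrong as written. They overcount event-free participants by one day. The exacerbation rate departs from the protocol by 1 − k days, and the COPDCompEx rate departs from the SAP's own sentence by one day throughout. The arithmetic is certain, and its effect on the rate ratio is negligible at about 0.001.

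The inconsistent end of follow-up is the part that could matter, and only if early intercurrent events with continued dosing differ between arms. The movement from about 0.72 to 0.69 at 5% versus 15% rests wholly on the simulation's assumptions and is not a forecast for this trial.

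Both rates are tertiary/exploratory. The primary log-rank and Cox analyses, the 194 events and the stated power do not use this offset. The correction is still worth making, because the appendix marks both rate tables (14.2.4.7 and 14.2.4.8) for the interim output that guides programme decisions. The amendment history mentions a filed note on the interim calculation, so the documents alone do not show which constant was used there.

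**What to change.** 1. In 4.2.10 and 4.2.11 use: time at risk = (end date − first dose + 1) − Σ over counted events of [min(event end + 14 or 7, end date) − event start]. This keeps every start day at risk, is right for any k under that rule, and still gives 1 day when an event spans the whole period. Amend the sentence in 4.2.10.1 to say that the start day is kept.
2. Define one end date and use it for both the event count and the time: the earlier of last dose and intercurrent event and, for COPDCompEx, also the last eDiary date. Count only events starting on or before it. This condition is needed. With last diary on day 84 and an exacerbation starting on day 120, counting that event would give 84 − (84 − 120) = 120 days, whereas leaving it out gives 84.
3. For these while-on-treatment rates, remove the sentence in 3.4.4 that includes data regardless of treatment discontinuation.

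The cost is two formulas, three short text edits and the matching programs, with nothing asked of participants. The downside is that a few exacerbations after the last diary leave the COPDCompEx rate. They still count in 4.2.11 if they precede last dose and any intercurrent event.

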4.2.10.4 Primary Analysis of Tertiary/Exploratory Endpoint

Number of COPDCompEx events, total follow-up time and annualised exacerbation rate including the two-sided 90% CI will be summarised by study intervention group.

The COPDCompEx event rate based on the period during the intervention from baseline through the last dose will be analysed using negative binomial regression (see Section 3.4.4). Rate ratio from AZD4831 compared to placebo will be displayed.

The analyses will be focused on the FAS population, including only those subjects with postbaseline eDiary data.

4.2.10.5 Sensitivity Analyses of the Tertiary/Exploratory Endpoint

Not applicable

4.2.10.6 Supplementary Analyses of the Tertiary/ Exploratory Endpoint

Not applicable

4.2.10.7 Subgroup Analyses

Not Applicable

4.2.11 Tertiary/Exploratory Endpoint – Annualised rate of moderate or severe COPD exacerbations

4.2.11.1 Definition

Defined in section 4.2.2.1. Events must be separated by at least 7 days in order to count as separate events.

4.2.11.2 Derivations

Annualised rate of moderate or severe COPD exacerbations based on the period during the intervention from baseline through the last dose will be calculated as follows:

Annualised rate of moderate or severe COPD exacerbations

Total number of moderate or severe COPD exacerbations

(Date of last dose of IP – Date of the first dose of IP – recovery time + 2)/365.25

Where recovery time is defined as:

$$\sum_{i=1}^{k} [min(i^{th} \ exacerbation \ end \ date + 7, date \ of \ last \ dose \ of \ study \ intervention)$$

$$- i^{th} \ exacerbation \ start \ date + 1]$$

For participants who do not experience an on-treatment moderate or severe COPD exacerbation event, date of censoring will be the date of last dose.

4.2.11.3 Handling of Dropouts

The "while on treatment" strategy, same as defined in section 4.2.2.3

4.2.11.4 Primary Analysis of Tertiary/Exploratory Endpoint

Number of moderate or severe AECOPD events, total follow-up time and annualised exacerbation rate including the two-sided 90% CI will be summarised by study intervention group.

Number of participants with at least one moderate or severe AECOPD, total number of days of exacerbations, total number of days of exacerbations per participant and total number of exacerbations per participant-treatment year will be summarised by study intervention group.

Annualised rate of moderate or severe COPD exacerbations based on the period during the intervention from baseline through the last dose will be analysed using negative binomial regression (see Section 3.4.4). Rate ratio from AZD4831 compared to placebo will be displayed.

The analyses will be focused on the FAS population.

